6.2.12. Blood and Urine Samples

Blood and urine for laboratory safety tests will be collected according to the Study Procedures Tables ([Appendix 2](#)). The volume of blood phlebotomized will be roughly 100 mL at screening and subsequently is not to exceed 200 mL every 3 months. CCI

The tests will be analyzed using standard procedures. All laboratory tests must be reviewed for clinical significance by the Investigator or qualified designee.

The analytes listed in [Table 6-1](#) will be tested.

6.2.13. Bone Marrow Assessment

For subjects without radiographic evidence of disease at screening, a bone marrow biopsy including aspirate is required within the screening window.

A bone marrow biopsy including aspirate is required at Week 25 for subjects who otherwise would meet criteria for a CR or complete remission with incomplete bone marrow recovery (CRi).

An additional bone marrow biopsy, including aspirate, may be obtained on protocol per investigator discretion following evidence of an improvement in clinical response.

Any bone marrow aspirate obtained should be sent for central MRD assessment, immunophenotyping, bio-banking, and follow-up research.

CCI

[REDACTED]

CCI

[REDACTED]

CCI

[Redacted]

[Redacted]

[Redacted]

[Redacted]

[Redacted]

[Redacted]

[Redacted]

CCI

[Redacted]

[Redacted]

CCI [REDACTED]	[REDACTED]	
[REDACTED]	[REDACTED]	

[REDACTED]

6.3. Assessments for Premature Discontinuation from Study

If a subject discontinues study dosing (for example, as a result of an AE), every attempt should be made to keep the subject in the study and continue to perform the required study-related follow-up and procedures (see Section 6.4 Criteria for Discontinuation of Study Treatment). If this is not possible or acceptable to the subject or investigator, the subject may be withdrawn from the study. Long-term follow-up within the GCLLSG registry is recommended.

6.4. Criteria for Discontinuation of Study Treatment

See Sections 3.4 and 3.5 for discontinuation criteria.

6.5. Dose Interruption and Reduction

The following are the guidelines for dose interruption and/or reduction. If an AE is attributed to study drug, the investigator's discretion will be used to determine if the drug not attributed to the AE will be withheld based on the investigator's assessment of risk-benefit of withholding the study drug.

Subjects who experience Grade 3 or 4 neutropenia whilst on idelalisib treatment must have their neutrophil count measured weekly until resolution to \leq Grade 2, per Table 6.2.

An interruption of tirabrutinib and/or idelalisib administration of up to 2 weeks will be acceptable to allow for any reversal of toxicity between doses of tirabrutinib and/or idelalisib. If the toxicity does not resolve to CTC Grade \leq 2 within 2 weeks, additional doses of the interrupted drug(s) will not be administered unless the toxicity is deemed related to the subject's underlying disease in the opinion of the investigator. If the toxicity is deemed to be related to one agent (tirabrutinib or idelalisib), the subject may resume the other drug as a single agent, however, the discontinued drug may not be re-initiated on this study.

A subject who discontinues obinutuzumab for any reason other than progression may remain on study receiving the combination of tirabrutinib and idelalisib as assigned.

Subjects experiencing a related or non-related AE at any point during the study that takes longer than 2 weeks to resolve will be reviewed on a case-by-case basis by the investigator and the sponsor. Upon resolution of the AE, or in the opinion of the Investigator if the AE is considered to be well controlled and if the subject is deemed to be gaining clinical benefit from treatment with tirabrutinib and/or idelalisib, a subject may continue to receive tirabrutinib and/or idelalisib at their assigned dose or at a lower dose (and consistent with Table 6-2). The dose may subsequently be increased back to the original dose level if considered safe to do so by the treating investigator and upon approval by the sponsor.

The dose modification instructions focus on the types of events most commonly attributed to each of the study agents. The recommendations provided in Table 6-2, and Table 6-3 comprise only guidelines; variations from these recommendations may be warranted based on an investigator's individual judgment in considering potential risks, benefits, and therapeutic alternatives available to each subject. **The exceptions are SJS/TEN or DRESS, Grade 4 ALT/AST with Bilirubin elevation, organizing pneumonia, symptomatic (Grade \geq 2) pneumonitis, PJP infection, and bowel perforation where idelalisib must be discontinued**

Table 6-2. Dose Adjustments, Withholding and Discontinuation Related to Idelalisib and/or Tirabrutinib

NCI CTCAE Grade	Recommendation	
	Idelalisib	Tirabrutinib
HEMATOLOGICAL ADVERSE EVENTS		
Neutropenia^a		
Grade ≤ 3 Neutropenia	Maintain current dose level and schedule. Blood counts must be monitored at least weekly until Grade ≤ 2.	Maintain current dose level and schedule.
Grade 4 neutropenia (or occurrence of neutropenic fever or infection)	Withhold until resolved to Grade ≤2. Consider G-CSF support. Tirabrutinib and idelalisib may be reinitiated either together or sequentially. Blood counts must be monitored at least weekly until ANC ≤ Grade 2. If the toxicity recurs, consider discontinuing idelalisib.	Withhold tirabrutinib until resolved to Grade ≤ 2. Consider G-CSF support. If the toxicity recurs, consider a decrease in tirabrutinib to 40 mg. If toxicity persists following discontinuation of idelalisib alone, discontinue tirabrutinib as well.
Thrombocytopenia		
Grade ≤ 3 Thrombocytopenia	Withhold for clinically significant bleeding.	
Grade 4 Thrombocytopenia	Withhold tirabrutinib and idelalisib until resolved to Grade 1 or baseline (recovery). Tirabrutinib and idelalisib may be reinitiated at the previous dose. If the toxicity recurs, consider a decrease in tirabrutinib to 40 mg or discontinuing tirabrutinib. If toxicity persists following discontinuation of tirabrutinib, discontinue idelalisib as well.	
NON-HEMATOLOGICAL ADVERSE EVENTS		
Rash		
Grade ≤ 2	Maintain current dose level and schedule.	
Grade 3 or 4	Withhold tirabrutinib and idelalisib until resolved to Grade 1 or baseline (recovery). Tirabrutinib and idelalisib may be resumed and a dose reduction to tirabrutinib 40 mg may be considered if multiply recurrent. If toxicity recurs following repeated rechallenge, discontinue tirabrutinib and/or idelalisib.	
Stevens-Johnson Syndrome (SJS), Toxic Epidermal Necrolysis (TEN) and Drug Reaction with Eosinophilia and Systemic Symptoms (DRESS).		
Any Grade	Discontinue Idelalisib and concomitant medications that have been associated with SJS/TEN and drug reaction with eosinophilia and systemic symptoms (DRESS). Institute systemic immunosuppression per institutional standards.	-

NCI CTCAE Grade	Recommendation	
	Idelalisib	Tirabrutinib
Bowel Perforation		
Any Grade	Discontinue idelalisib.	Maintain current dose level and schedule.
Progressive Multifocal Leukoencephalopathy (PML)		
Any Grade	Withhold idelalisib until PML is excluded. Refer to section 6.6.11	-
Diarrhea		
Grade \geq 1	In the absence of evidence of infection, provide anti-diarrheal (eg, loperamide) and maintain current tirabrutinib and idelalisib dose level and schedule.	
Grade 2	Withhold idelalisib until Grade \leq 1. Consider anti-diarrheal (eg, loperamide). Resume idelalisib at previous dose level. If rechallenge results in recurrence, discontinue idelalisib. Consider addition of anti-inflammatory (eg, budesonide).	Withhold tirabrutinib until resolved to Grade \leq 1. If resolution occurs within 7 days, tirabrutinib may be reinitiated at the previous dose. If the toxicity recurs or is persistent with corticosteroid therapy, decrease to 40 mg.
Grade 3 or 4	Withhold idelalisib until resolved to Grade 1 or baseline (recovery). Rule out infectious etiology including CMV (see Section 6.2.10.1). Consider anti-diarrheal (eg, loperamide) and/or addition of anti-inflammatory agent (eg, sulfasalazine, budesonide). If toxicity persists or recurs upon repeated rechallenge, permanently discontinue idelalisib. Refer to Section 6.2.10.1 for evaluation.	Withhold tirabrutinib until Grade \leq 1. Consider anti-diarrheal (eg, loperamide) and/or addition of anti-inflammatory agent (eg, sulfasalazine, budesonide).
Hepatic Adverse Events (elevations in ALT, AST or bilirubin)		
Grade 1 (ALT/AST \leq 3 \times ULN) (Bilirubin \leq 1.5 \times ULN)	Maintain current dose level and schedule.	
Grade 2 (ALT/AST > 3-5 \times ULN) (Bilirubin > 1.5 - \leq 3 \times ULN)	Maintain current dose level and schedule. Monitor ALT, AST, ALP, and bilirubin at least 1 \times per week.	
Grade 3 (ALT/AST > 5-20 \times ULN) (Bilirubin > 3-10 \times ULN)	Withhold all study medication. Monitor ALT, AST, ALP, and bilirubin at least 1 \times per week until all abnormalities are Grade \leq 1 or baseline. If bilirubin abnormality was Grade < 3, resume tirabrutinib and idelalisib at previous dose level and resume obinutuzumab. If bilirubin abnormality was Grade \geq 3, discontinue idelalisib and obinutuzumab.	
Grade 4 (ALT/AST > 20 \times ULN) (Bilirubin > 10 \times ULN)	Withhold all study medication. Monitor ALT, AST, ALP, and bilirubin at least 1 \times per week until all abnormalities are Grade \leq 1 or baseline. If bilirubin abnormality was Grade < 3, resume tirabrutinib only. If bilirubin was Grade 4, discontinue all study medication.	

NCI CTCAE Grade	Recommendation	
	Idelalisib	Tirabrutinib
Organizing Pneumonia		
Any Grade	Discontinue idelalisib permanently. Institute supportive care as appropriate.	
Pneumonitis		
Grade 1	Withhold all study medication until resolution to baseline. May resume therapy at investigator discretion.	
Grade 2	Discontinue all study medication. Supportive care, including oxygen or mechanical ventilation, should be considered early and provided as necessary. May consider resuming therapy with tirabrutinib alone after discussion with medical monitor.	
Grade 3 or 4	Discontinue all study medication permanently, institute systemic corticosteroids and supportive care per institutional standard.	
PJP infection		
Any Grade	Discontinue idelalisib. Consider discontinuation of tirabrutinib until the infection has resolved.	
Unequivocal CMV infection^a		
Any Grade	Discontinue idelalisib. Consider discontinuation of tirabrutinib until the infection has resolved. If the benefits of resuming idelalisib are judged to outweigh the risks, consideration should be given to administering pre-emptive CMV therapy.	
Hypersensitivity		
Any Grade	Consider interrupting or discontinuing tirabrutinib treatment (see Section 6.6.2).	
OTHER NON-HEMATOLOGICAL ADVERSE EVENTS		
Grade 1	Maintain current dose level and schedule	
Grade 2	Withhold tirabrutinib and idelalisib until Grade \leq 1 or baseline. May resume idelalisib with tirabrutinib at initial or lower dose level or discontinue tirabrutinib and idelalisib at investigator discretion.	
Grade 3	Withhold tirabrutinib and idelalisib until Grade \leq 1 or baseline. May resume idelalisib with tirabrutinib at lower dose level or discontinue tirabrutinib and idelalisib at investigator discretion.	
Grade 4	Discontinue tirabrutinib and idelalisib.	

a) CMV should be diagnosed using clinical or laboratory criteria per established institutional standard

Table 6-3. Dose Adjustment Guidelines for Subjects Receiving Obinutuzumab

NCI CTCAE Grade	Recommendation
	Toxicity attributable to obinutuzumab
HEMATOLOGICAL ADVERSE EVENTS*	
Neutropenia^a	
Grade ≤ 2 neutropenia	Maintain current dose level and schedule.
Grade 3 neutropenia	Maintain current dose level and schedule. Consider G-CSF support.
Grade 4 neutropenia (or occurrence of neutropenic fever or infection)	Delay obinutuzumab until Grade ≤ 2 (ANC ≥ 1 × 10 ⁹ /L) and/or neutropenic fever or infection is resolved; thereafter, resume at full dose. Consider G-CSF support to avoid delays. If delay is > 4 weeks, discontinue obinutuzumab.
Thrombocytopenia	
Grade ≤3	Maintain current dose level and schedule.
Grade 4	Delay obinutuzumab until Grade ≤ 3 (platelets ≥ 25 × 10 ⁹ /L); thereafter, resume at full dose. If delay is > 4 weeks, discontinue obinutuzumab, unless the Grade 4 thrombocytopenia occurred after the first 3 weekly doses.
Hemorrhage	
N/A	
Hold obinutuzumab in case of platelets < 20,000/μL. If Day 8 is delayed then skip Day 8 and administer Day 15 as previously scheduled (if symptomatic bleeding has resolved). If Day 15 is delayed then skip Day 15 dosing and administer Day 29 of obinutuzumab as scheduled.
 
At the discretion of the study investigator, for subjects who are on low molecular weight heparin (LMWH), when thrombocytopenia with platelets <20,000/μL develops, reduce the dose of LMWH or new oral anticoagulants (NOAC) used.
 
Hold tirabrutinib and obinutuzumab for clinically significant bleeding (irrespective of platelet count) until it resolves.

NON-HEMATOLOGICAL ADVERSE EVENTS	
Cutaneous	
Grade ≤2	Maintain current dose level and schedule.
Grade 3 or 4	Delay obinutuzumab until Grade ≤ 1; thereafter, may resume at full dose or discontinue obinutuzumab at investigator discretion.
Gastrointestinal Inflammation/Diarrhea	
Grade ≤1	Maintain current dose level and schedule.
Grade 2	Maintain current dose level and schedule.
Grade 3	Hold idelalisib and obinutuzumab until subject is sufficiently stable to receive further treatment; thereafter maintain full dose and schedule. If recurrent with rechallenge, consider treatment with tirabrutinib alone.
Grade 4	Delay all study medication until subject is sufficiently stable to receive further treatment; if recurrent with rechallenge, consider treatment with tirabrutinib alone.

NCI CTCAE Grade	Recommendation
	Toxicity attributable to obinutuzumab
Hepatic Adverse Events (elevations in ALT, AST, or bilirubin)	
Grade ≤1 (ALT/AST≤3×ULN) (Bilirubin≤1.5×ULN)	Maintain current dose level and schedule.
Grade 2 (ALT/AST>3-5×ULN) (Bilirubin>1.5-≤3×ULN)	Maintain current dose level and schedule.
Grade 3 (ALT/AST>5-20×ULN) (Bilirubin>3-10×ULN)	Withhold all study medication. Monitor ALT, AST, ALP, and bilirubin at least 1× per week until all abnormalities are Grade ≤ 1 or baseline. If bilirubin abnormality was Grade < 3, resume tirabrutinib and idelalisib at previous dose level, resume obinutuzumab. If bilirubin abnormality was Grade ≥ 3, discontinue idelalisib and obinutuzumab.
Grade 4 (ALT/AST>20×ULN) (Bilirubin>10×ULN)	Withhold all study medication. Monitor ALT, AST, ALP, and bilirubin at least 1× per week until all abnormalities are Grade ≤ 1 or baseline. If bilirubin abnormality was Grade < 3, resume tirabrutinib. If bilirubin was grade 4, discontinue all study medication.
Pneumonitis	
Grade ≤1	Maintain current dose level and schedule.
Grade 2	Withhold all study medication until Grade ≤ 1, consider systemic corticosteroids. May consider resuming therapy with tirabrutinib alone
Grade ≥3	Delay obinutuzumab as necessary to ensure subject is sufficiently stable to receive further treatment; thereafter maintain full dose and schedule or discontinue obinutuzumab at investigator discretion.
Hypersensitivity	
Any Grade	Stop the infusion and discontinue obinutuzumab treatment (see section 6.6.2)
OTHER NON-HEMATOLOGICAL ADVERSE EVENTS	
Grade ≤2	Maintain current dose level and schedule.
Grade ≥3	If felt to be related to obinutuzumab, delay obinutuzumab as necessary to ensure subject is sufficiently stable to receive further treatment; thereafter maintain full dose and schedule or discontinue obinutuzumab at investigator discretion.

Abbreviations: ALP alkaline phosphatase, ALT alanine aminotransferase, AST aspartate aminotransferase, ANC absolute neutrophil count, CTCAE Common Terminology Criteria for Adverse Events, G CSF granulocyte colony stimulating factor, NCI National Cancer Institute, ULN upper limit of normal

- a Neutropenia and thrombocytopenia should not necessarily lead to delay in dosing of obinutuzumab or idelalisib if it is believed that the cytopenia is due to CLL, and not to the drug(s).

6.6. Recommendations for Evaluation, Intervention, and Drug Discontinuation for Specific Adverse Events or Conditions

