6.6.4. Hepatic Events

Transaminase Elevations: Reversible asymptomatic ALT/AST increases have been observed with idelalisib in subjects with hematologic malignancies. Transaminase elevations generally occurred within 4 to 12 weeks of drug initiation, and resolved spontaneously over a period of 2 to 4 weeks with drug being continued for Grade 1 and 2 elevations and drug withheld for Grade 3 or 4 elevations until resolution. Transaminase elevations are most frequently asymptomatic, transient and occurring within the first 3 months of treatment.

Successful rechallenge after resolution at either the same or lower dose level of idelalisib has been achieved in the majority of subjects. There has been no evidence of impaired synthetic function. Close monitoring of hepatic laboratory tests during therapy is important to allow for appropriate idelalisib interruption and reinstatement so that subjects may continue with study drug treatment.

HBV Reactivation: HBV reactivation can occur with treatment, most commonly in patients treated with obinutuzumab. The risk is very low among patients with negative anti-HBc serology and/or undetectable HBV DNA as assessed by quantitative PCR. Although some subjects who are HBc antibody positive with negative PCR may have had passive transfer of antibody from intravenous IgG, it cannot be known for certain that any such subject did not have natural HBV infection. Therefore, all subjects who are HBc antibody positive at screening will be monitored for potential HBV reactivation (manifest as detectable HBV DNA by quantitative PCR). Surveillance of subjects who test positive for HBc antibody for HBV reaction will be performed according to the Study Procedures Table ([Appendix 2](#)). If there is evidence of HBV reactivation immediately stop study treatment and start appropriate treatment for HBV. In the event of HBV reactivation, please contact the Medical Monitor prior to re-initiation of study treatment.

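### Protocol Section 6.5 gives opposite instructions on restarting tirabrutinib or idelalisib when drug-related toxicity is still above Grade 2 after a two-week interruption and later resolves or is controlled

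*Protocol*

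**What the plan says.** The third paragraph of Protocol Section 6.5 opens with a limit: "An interruption of tirabrutinib and/or idelalisib administration of up to 2 weeks will be acceptable". It then gives the consequence of exceeding it. Where toxicity has not fallen to CTC Grade 2 or lower within two weeks, "additional doses of the interrupted drug(s) will not be administered unless the toxicity is deemed related to the subject's underlying disease". If one of the two oral agents is held responsible, the other may be resumed alone, but "the discontinued drug may not be re-initiated on this study".

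The fifth paragraph of the same section starts from a wider trigger: "Subjects experiencing a related or non-related AE at any point during the study that takes longer than 2 weeks to resolve". Such subjects "will be reviewed on a case-by-case basis by the investigator and the sponsor". Once the event has resolved, or is well controlled in a subject judged to be benefiting, "a subject may continue to receive tirabrutinib and/or idelalisib at their assigned dose or at a lower dose". This must be consistent with Table 6-2, and the dose may later be raised again with sponsor approval.

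Neither paragraph refers to the other. The section introduces its content as guidelines. The sentence in Section 6.5 that allows investigators to vary from the recommendations names Tables 6-2 and 6-3 only.

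**The concern.** A site that reads the third paragraph stops the drug for good. A site that reads the fifth may restart it after review. Both would be following the protocol.

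This is more than untidy wording. Protocol Section 3.4 lists unacceptable toxicity as a reason to discontinue treatment and defines it by pointing to Section 6.5, so the conflict sits inside a discontinuation criterion. The SAP then reports what sites did. Section 4.1 tabulates completion and discontinuation, with reasons, for each drug. Section 7.1.6.1 tabulates adverse events leading to discontinuation, dose modification and interruption for each drug. Section 4.2.2 adjusts expected dosing for interruptions made as the protocol specifies. The same event could therefore be treated, counted and adjusted for differently from one site to another, in a study whose secondary objective is safety and tolerability.

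**Working it through.** No arithmetic applies. The check is whether one subject can meet both rules and receive different answers.

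**Step 1. The two rules side by side (Protocol Section 6.5).**

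| | Third paragraph | Fifth paragraph |
|---|---|---|
| Trigger | Toxicity not down to Grade 2 or lower within two weeks of interruption | Any adverse event, related or not, taking more than two weeks to resolve |
| Exception | Toxicity due to the underlying disease | None stated |
| Process | None stated beyond the investigator's judgement of disease-relatedness | Review by investigator and sponsor |
| Outcome | No further doses of the interrupted drug(s); an agent held responsible is not restarted on study | Oral drug(s) may continue at the assigned or a lower dose, with possible later re-escalation |

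**Step 2. A test case.** Take a Grade 3 transaminase elevation attributed to idelalisib, with bilirubin below Grade 3. The drug is held, the event is still Grade 3 at day 14, and it resolves in week 4. The third paragraph is triggered and its disease exception does not apply, so there are no further doses of idelalisib. The fifth paragraph is also triggered, because the event is related and lasted over two weeks. On resolution, idelalisib may be given again after review. The answers are opposite.

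**Step 3. Does the reference to Table 6-2 settle it?** It narrows the conflict. Where the table itself requires discontinuation (organizing pneumonia, for example), or allows only tirabrutinib to resume (Grade 4 ALT/AST with bilirubin below Grade 3), the fifth paragraph cannot support restarting idelalisib. It does not remove the conflict. The rows for Grade 3 hepatic events (bilirubin below Grade 3), Grade 4 thrombocytopenia and Grade 3 or 4 rash hold drug until Grade 1 or baseline and then permit resumption, with no time limit. Table 6-3 does set a limit for obinutuzumab (discontinuation after a delay of more than 4 weeks for Grade 4 neutropenia and, with an exception, Grade 4 thrombocytopenia). Silence on time is therefore not the convention across both tables.

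**Step 4. Recovery grade.** The third paragraph asks for Grade 2 or lower, whereas the rows just named ask for Grade 1 or baseline. A subject with a Grade 3 hepatic event that is Grade 2 on day 14 clears the third paragraph's bar, yet must still be held under the table, past the two weeks that the third paragraph calls acceptable.

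**Step 5. Is the case plausible?** Protocol Section 6.6.4 says transaminase elevations "resolved spontaneously over a period of 2 to 4 weeks", with drug withheld for Grade 3 or 4, and it expects idelalisib to be interrupted and reinstated. Section 6.6.3 gives a median time to resolution of severe diarrhea of between 1 week and 1 month across trials. Both ranges extend past two weeks. They are times to resolution, not times to Grade 2, so they show that the case can occur and not how often.

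**The case against.** The strongest defence is that the two paragraphs cover different subjects. The fifth speaks of continuing a drug, not re-initiating it. It has real work to do without touching the third: unrelated events, events with no interruption, events already at Grade 2 or lower after two weeks, and continuing whichever agent was not stopped. That is right for most of its scope, and it confines the conflict to the group tested above. It does not clear that group. The permission takes effect upon resolution of an event that may be drug-related, and it refers to a table that governs the resumption of withheld drugs. Reading it as limited to drugs never interrupted fits poorly with both.

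A second defence is that Section 6.5 is only guidance. That label sets no order of precedence, and the wording in the third paragraph is prohibitive.

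A third is that the two-week limit can simply be laid over a table that is silent on time. That is possible, and silence alone is not a contradiction. But the documents do not say so, and the fifth paragraph points the other way.

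Stronger readings that a reader might infer do not hold:

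- *Every toxicity unresolved at two weeks is caught.* The bar depends on Grade 2, not on full resolution, and it has an exception for underlying disease.
- *Table 6-2 always holds to Grade 1 with no time limit.* Grade 4 neutropenia is held to Grade 2 or lower, and the tirabrutinib row for Grade 2 diarrhea has a 7-day condition.
- *About 9 Arm B subjects are affected.* Protocol Section 1.4 reports Grade 3 or higher ALT increase in 31% of 32 subjects given idelalisib with obinutuzumab, and 0.31 × 30 = 9.3. That is the incidence of the event, not of the event persisting above Grade 2 at day 14. It includes Grade 4, and it comes from 150 mg twice daily in previously untreated CLL, a population that Section 1.6 calls distinct from this one.
- *The primary result is undermined.* Subjects who stop all treatment before Week 25 without progression still have the Week 25 visit (Protocol Section 6.7). Treated subjects stay in the Full Analysis Set under their planned treatment (SAP Section 3.1.2). No inferential test is planned (Protocol Section 8.5.1).

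**Conclusion.** The contradiction is real but narrow. It covers subjects with drug-related toxicity still above CTC Grade 2 after a two-week interruption of tirabrutinib and/or idelalisib, whose event later resolves or is well controlled, and for whom Table 6-2 does not itself require the drug to stop. For them Section 6.5 both forbids and permits further dosing, with no stated precedence.

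The documents give no rate for this group, so its size cannot be stated. The consequence is inconsistent treatment and inconsistent reporting of discontinuations, interruptions and exposure. Staying on the combination may influence a subject's chance of complete remission at Week 25, but the documents do not allow that effect to be measured, and the validity of the planned estimate is not in question.

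The conclusion rests on reading the fifth paragraph as covering drugs that have been interrupted, which is the better fit to its wording. It should be corrected. No view is taken on which rule is clinically right.

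**What to change.** Reconcile the third and fifth paragraphs of Section 6.5 with each other and with Table 6-2, so that one rule governs interruptions of the oral drugs beyond two weeks. The text should state:

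- the recovery grade that counts, and whether it is common to all toxicities or set row by row in Table 6-2;
- whether review by investigator and sponsor is an exception to the bar on further doses and, if so, for which events;
- whether the two-week limit applies to Table 6-2 rows that give no time limit.

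The sponsor decides which rule stands. The cost is a protocol clarification, with no change to sample size, endpoints or analysis method. If subjects have already been managed under the present text, the study report should say which rule was followed for any interruption longer than two weeks, so that the per-drug discontinuation and interruption tables can be read correctly.

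### Table 6-2 heads its first diarrhea row Grade ≥ 1 and says to maintain both oral drugs, which contradicts the Grade 2 and Grade 3 or 4 rows that withhold them; Grade 1 was evidently meant.

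*Protocol*

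**What the plan says.** Protocol Section 6.5, Table 6-2, gives dose guidance for the two oral drugs. Its diarrhea block has three rows.

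- **First row, headed Grade ≥ 1, both drugs:** "In the absence of evidence of infection, provide anti-diarrheal (eg, loperamide) and maintain current tirabrutinib and idelalisib dose level and schedule". The heading and the start of the instruction read together as "Grade \geq 1 In the absence of evidence of infection".
- **Grade 2, idelalisib:** "Withhold idelalisib until Grade \leq 1. Consider anti-diarrheal (eg, loperamide). Resume idelalisib at previous dose level".
- **Grade 2, tirabrutinib:** "Withhold tirabrutinib until resolved to Grade \leq 1. If resolution occurs within 7 days, tirabrutinib may be reinitiated at the previous dose".
- **Grade 3 or 4, idelalisib:** "Withhold idelalisib until resolved to Grade 1 or baseline (recovery). Rule out infectious etiology including CMV".
- **Grade 3 or 4, tirabrutinib:** "Withhold tirabrutinib until Grade \leq 1".

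The text of Section 6.5 before the table says that the recommendations in Tables 6-2 and 6-3 are guidelines from which an investigator may depart. It then lists the events for which stopping idelalisib is mandatory, and diarrhea is not among them. Section 6.5 gives no rule for which row prevails when two rows apply.

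**The concern.** Read literally, Grade ≥ 1 takes in every grade of diarrhea. The first row would then tell the investigator to keep giving both drugs with an anti-diarrheal at Grades 2, 3 and 4, provided there is no evidence of infection. The rows below tell the same investigator to stop both drugs.

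The subject matter gives the wording some weight. Diarrhea was the most frequent adverse event in the supporting Phase 1b combination study (35% of subjects, Protocol Section 1.3.4). Section 6.6.3 says that severe diarrhea from idelalisib responds poorly to antimotility drugs, and it describes resolution after idelalisib is interrupted. Applied to Grade 3 or 4, the first row as printed would recommend the reverse of that experience.

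What is at stake is the clarity of a dosing threshold. The SAP (Section 7.1.7) does list diarrhea as an adverse event of interest and will tabulate such events that lead to dose modification or interruption, but that table is descriptive.

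**Working it through.** No formula applies. The check lists which rows cover each grade, then looks for evidence of the intended heading.

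**1. Coverage of each grade in the Table 6-2 diarrhea block, no evidence of infection**

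| Grade | Rows that apply as printed | Instruction for the oral drugs | Rows that apply if the first heading is Grade 1 |
|---|---|---|---|
| 1 | Grade ≥ 1 | maintain | Grade 1 |
| 2 | Grade ≥ 1; Grade 2 | maintain; withhold | Grade 2 |
| 3 | Grade ≥ 1; Grade 3 or 4 | maintain; withhold | Grade 3 or 4 |
| 4 | Grade ≥ 1; Grade 3 or 4 | maintain; withhold | Grade 3 or 4 |

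As printed, the rows cover {1, 2, 3, 4}, {2} and {3, 4}. With Grade 1 in the first heading they cover {1}, {2} and {3, 4}, with no overlap and no gap. Grade ≤ 1 gives the same result for any event that carries a grade.

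**2. Does the infection condition separate the rows?** It does not. The Grade 2 row suggests adding an anti-inflammatory and stopping idelalisib if rechallenge brings the event back. The Grade 3 or 4 row asks for infection to be ruled out and then suggests anti-inflammatory treatment. Both rows are therefore written with non-infectious diarrhea in view, which is the same situation the first row addresses.

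**3. Evidence for the intended heading**

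- *Resumption threshold.* In the Grade 2 row both drugs stay withheld until Grade ≤ 1. In the Grade 3 or 4 row idelalisib is withheld until Grade 1 or baseline, and tirabrutinib until Grade ≤ 1. A drug that may restart at Grade 1 fits a row that maintains at Grade 1. It does not fit a row that maintains at every grade.
- *Other non-hematological events, Table 6-2.* The Grade 1 row maintains the dose. The Grade 2 row says "Withhold tirabrutinib and idelalisib until Grade \leq 1 or baseline. May resume idelalisib with tirabrutinib at initial or lower dose level". This is the same pattern with unambiguous headings.
- *Table 6-3, "Gastrointestinal Inflammation/Diarrhea".* This block opens at Grade ≤ 1 with the dose maintained. Table 6-3 concerns toxicity attributed to obinutuzumab, so it is evidence of the drafting pattern only and not an instruction for the oral drugs here.
- *Direction of the sign in other opening rows.* Three other blocks in Table 6-2 (neutropenia, thrombocytopenia, rash) and seven in Table 6-3 open with an inequality sign, 3 + 7 = 10 in all, and each uses ≤.

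**4. Reliability of the printed sign.** The ≤ signs in neighbouring cells of the same diarrhea block make sense, and so do the ≥ signs elsewhere in Section 6.5, such as the Grade ≥ 2 pneumonitis exception and the bilirubin rule. No other part of the protocol corrects the heading.

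**The case against.** **The point rests on one character.** Text extracted from a PDF can lose or alter symbols. The protocol copy of the Appendix 2 footnote on the bone marrow window lacks the minus sign that the SAP copy shows, and the MRD threshold reads 10 to the power 4 in the protocol where the SAP has a negative exponent. Those are dropped symbols rather than reversed ones, and the surrounding ≤ and ≥ signs read correctly. A misread still cannot be excluded. The pattern of the other headings shows what was meant, but it does not show whether the slip is in the sponsor's document. This part of the objection stands, so the source has to be checked before anything is changed.

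**The table resolves itself.** Grades 2, 3 and 4 are named in explicit withhold rows, and most readers would follow the more specific row. The tables are guidance, and Section 7.5 brings treatment-emergent toxicities to the medical monitor. This stands as a limit on harm. It does not make the heading right, because the protocol states no precedence rule and the infection condition could lead a reader to treat the first row as the specific one.

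**A reader might infer that this is the only overlapping block in the dose tables.** The documents do not support that. In Table 6-2, Grade 3 neutropenia falls in the maintain row, yet neutropenic fever or infection is placed with Grade 4 in the withhold row. Table 6-3 has the same structure, with maintain at Grade 3 and delay for fever or infection. Grade 3 neutropenia with fever or infection therefore meets two rows in both tables. There, too, the natural reading is that the more specific condition governs.

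**A reader might also take total enrollment, about 36 subjects, as the number at risk.** That is only the number to whom Table 6-2 could apply. The documents do not allow a count of subjects who would be dosed wrongly, and the three doubly covered grades describe wording rather than patients.

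**Conclusion.** The inconsistency holds as printed. The first diarrhea row of Table 6-2 contradicts the two rows beneath it for non-infectious diarrhea above Grade 1, and Grade 1 (or Grade ≤ 1) was evidently intended.

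It is a low-severity drafting error in an operative dosing table. Any practical risk lies mainly at Grade 2, where continuing treatment with loperamide would look least unreasonable to an investigator. No sample size, endpoint, analysis set or confidence interval depends on it.

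The conclusion assumes that the sign in the source PDF is ≥. If the source shows ≤, there is nothing to correct.

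**What to change.** Check the sign in the source PDF. If it is ≥, change the heading of the first diarrhea row in Table 6-2 to Grade 1 (or Grade ≤ 1). Each grade then has one instruction: maintain at Grade 1, and withhold at Grade 2 and at Grade 3 or 4.

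The cost is one table heading. Protocol Section 9.2.1 requires ethics committee submission and documented approval for modifications, so the change should travel with the next amendment and does not justify one of its own. The SAP is already based on amendment 6, and a further amendment may not be planned. If dosing has ended, the benefit is limited to correcting the record and keeping the heading out of later protocols that reuse the table.
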